### Study Hypotheses:

[figure not shown]
Study Hypothesis 1: Participants in the COMPASSgoal group will have higher TBI self-efficacy and higher community integration scores over time than participants in the supported discharge group matched on executive dysfunction score;

Study Hypothesis 2: *Individual psychosocial profile (emotional status, resilience, and level of post-traumatic stress disorder, PTSD) will mediate the responsiveness to the COMPASSgoal intervention, measured through the standardized experimental performance of everyday tasks, in Veterans with impaired executive function due to TBI.*

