### **Hypothesis 2: Psychosocial Profile as Mediator of the Responsiveness to the Intervention Over Time Course**

To explore Hypothesis 2, we will utilize a multistage analytic strategy. Because of the possibility of missing data due to non-responses, missed visits, attrition, and mortality over the course of the study, the statistical analysis presents certain challenges. At the first stage, a linear mixed model will be used to incorporate all available data, evaluate trends, and estimate change of outcome variables without discarding cases that have missing data points. Furthermore, linear mixed models (LMM) control for confounding effects of other repeatedly measured covariates while accounting for the correlation among repeatedly measured outcomes. SAS PROC MIXED will be used to estimate a LMM for each outcome of interest. For categorical outcomes, generalized estimating equations (GEEs) will be used to evaluate trends over time while accounting for the dependency among the repeatedly measured outcomes. GEEs will be solved using SAS PROC GENMOD.

Also for **Hypothesis 2** analysis the following will be considered:

- Linear mixed models (LMM) will be used to control for confounding effects of other repeatedly measured covariates while accounting for the dependency among the repeated measured outcomes and covariance matrix.
- We will construct a model which only includes the repeated measures variables to obtain means, variances, and covariances.
- We will add time-invariant variables such as treatment group into the multi-level model (MEME) to predict the change over time in executive dysfunction and associated real-life task performance. Therefore, this method will allow us to address individual growth, identify latent trajectories of growth, relate the observed changes to pre-existing differences between TBI subjects, and determine treatment effects.

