Then, we will use linear growth curves to assess individual differences as well as group differences by following a two-stage LGM. At the second stage, we will construct a model that only includes the repeated measures variables to obtain means, variances, and covariances. At stage three, we will add time-invariant variables such as age, gender, and education into the model to predict change over time in executive function and real-world performance. We will also be able to refine our model at any level by assessing the fit after additional variables are inserted. The obtained covariance structure will allow us to draw inferences with regards to linear increases or decreases in executive dysfunction and real-world performance over time. Therefore, this method will allow us to address individual growth, identify latent trajectories of growth, and finally, relate the observed changes to pre-existing differences between TBI subjects.

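### The Hypothesis 2 growth model may be refined by fit from an open list of variables, and nothing in the plan accounts for that search when inference is drawn

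*Combined protocol and SAP*

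**What the plan says.** The SAP section on Hypothesis 2 describes several stages. Mixed models come first: "SAS PROC MIXED will be used to estimate a LMM for each outcome of interest". The number of outcomes is not fixed. Linear growth curves follow, and at stage three "we will add time-invariant variables such as age, gender, and education into the model to predict change over time". The wording leaves the list open. The next sentence lets the team "refine our model at any level by assessing the fit after additional variables are inserted". No fit statistic, entry or removal threshold, stopping rule or validation step is given, and no model is named as the one to be reported.

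The growth model is meant for inference. The SAP says its covariance structure "will allow us to draw inferences with regards to linear increases or decreases in executive dysfunction and real-world performance over time", and that the method will "relate the observed changes to pre-existing differences between TBI subjects".

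The hypothesis itself reads: "Individual psychosocial profile (emotional status, resilience, and level of post-traumatic stress disorder, PTSD) will mediate the responsiveness". That names three psychosocial characteristics in addition to the three demographic ones at stage three.

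On multiplicity, the SAP Overview promises Bonferroni adjustment in a sentence placed directly after the ANOVA and repeated measures ANOVA tests. It does not define the family of tests.

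**The concern.** When variables are tried and then kept or dropped by how well they fit, those that survive look stronger than they are. Ordinary p-values from the surviving model treat it as if it had been fixed in advance. A Bonferroni divisor that counts only the survivors has the same fault, because it ignores the variables tried and discarded.

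The claim at risk is that some characteristic of the Veterans predicts how they change over time, which is close to what Hypothesis 2 asserts. The protocol expects study findings to feed clinical practice guidelines (COMPASS Procedures and Implementations), so a chance predictor could be carried into practice advice.

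**Working it through.** **Sample size for the check.** The plan states no error rate, power or sample size for Hypothesis 2. Its only computed figure is for Hypothesis 1: 44 per group for 90% power at a standardized effect of 0.71, two-sided alpha 0.05. By the normal approximation, 2 × (1.960 + 1.282)² / 0.71² = 41.7, so 42 per group. Exact t-test power at 44 per group is 90.9%. 88 / (1 − 0.20) = 110. The figure reproduces, and 88 is used below as the evaluable sample.

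**Number of candidates, k.** k = 3 is age, gender and education. k = 6 adds the three characteristics in the Hypothesis 2 statement. The SAP does not name those three as stage-three candidates, so k = 6 is a plausible reading of an open list, not a count given in the plan.

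**Plain multiplicity, no search.** The chance of at least one p<0.05 among k independent null tests is 1 − 0.95^k.
- k = 3: 1 − 0.857 = 14.3%
- k = 6: 1 − 0.735 = 26.5%

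Bonferroni over the whole list, 1 − (1 − 0.05/k)^k, gives 4.9% in both cases.

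**With a fit-driven search.** The criterion is an assumption; AIC and BIC are both shown. Forward selection was simulated with k independent null candidates and n = 88. An ordinary regression on a per-subject change score stood in for the growth model. Entries are the chance of at least one false finding; simulation error is about one percentage point.

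| k | Criterion | Unadjusted | Bonferroni over retained terms | Bonferroni over all candidates |
|---|---|---|---|---|
| 3 | AIC | 15% | 12–13% | 5–6% |
| 3 | BIC | 11% | 11% | 5% |
| 6 | AIC | 28–29% | 20% | 5–6% |
| 6 | BIC | 20–21% | 20–21% | 5–6% |

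**Check of the BIC rows by formula.** BIC admits a first term when n × ln(1 + F/86) exceeds ln 88 = 4.477, that is when F > 86 × (e^(4.477/88) − 1) = 4.49. For a null term on 1 and 86 degrees of freedom the probability is 0.037. Then 1 − 0.963³ = 10.7% and 1 − 0.963⁶ = 20.2%, in line with the simulation. The entry threshold is stricter than p<0.05, so in the simulation every null term that BIC retained also showed p<0.05.

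**Reading the table.** Bonferroni holds near 5% only when its divisor counts every variable tried. That needs a closed list, which the plan does not give.

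**The case against.** The other side has several sound points.

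- A reader might infer that the plan commits to reporting unadjusted p-values for selected predictors. It does not; it is silent on how p-values after refinement are reported.
- A reader might infer that the search is for predictors of response to COMPASS, or that the treatment effect comes from the refined model. Neither is written. No variable-by-arm term is specified. The phrase "determine treatment effects" closes the multi-level model bullet; the growth-curve paragraph repeats that bullet's other purposes but leaves this one out.
- Most of the unadjusted excess is ordinary multiplicity. AIC search gives about 15% against 14.3% (k = 3) and 28–29% against 26.5% (k = 6), and BIC gives less than plain multiplicity. Locking the model without adjusting would therefore not help.
- The section opens "To explore Hypothesis 2, we will utilize a multistage analytic strategy", and checking fit while building a growth model is normal practice.
- The Bonferroni sentence could be read to cover these tests.

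The first three points stand and limit the claim. The fourth does not settle it: Overall Study Design presents both hypotheses as ones the study will test and uses the same language of exploring for the randomized comparison under Hypothesis 1. Nothing labels refined results as exploratory. The fifth helps only if the family includes every variable tried, and the text does not say so either way.

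**Conclusion.** The concern holds in a limited form. The SAP permits fit-driven refinement from an open list, intends inference from the model, and has no stated means of accounting for the search. With three to six null candidates the chance of at least one false predictor is about 11–29% unadjusted. It is about 11–21% if Bonferroni counts only the retained terms, against about 5% for Bonferroni over a locked list.

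These figures assume independent candidates, selection by AIC or BIC, 88 evaluable Veterans, one outcome, and a change-score regression in place of the growth model. More candidates or more outcomes would raise them.

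This is a minor point. The primary outcome, the randomized comparison under Hypothesis 1 and its sample size are untouched.

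**What to change.** Before arm-level data are seen, write into the SAP one locked Hypothesis 2 model for each named outcome. It should contain arm, visit, arm-by-visit, the baseline psychosocial terms under test, and age, gender and education. Name the measure behind each psychosocial term and write each term in the form in which it will be tested.

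Apply the Bonferroni adjustment already promised over all listed terms under test, and state whether the family spans outcomes. With three terms the threshold is 0.05/3 = 0.0167; with six it is 0.05/6 = 0.0083. Report this model as the Hypothesis 2 result. Models refined by fit can still be shown, labelled exploratory and without p-value claims.

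The timeline sets an interim analysis 13 months into the project. The lock should precede it, or the SAP should record what had been seen.

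The cost is wording only. The small downside is a stricter threshold per term and less freedom to simplify the reported model.

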### **Missing Data**

[figure not shown]
Rigorous methods to **address loss to follow-up and missing data** will also likely be of importance. As in many studies with vulnerable populations, participant dropout or censoring may be informative. For example, sicker patients and those with sub-optimal treatment results may opt to discontinue participating or providing samples or questionnaire responses. Thus, the probability of missing outcome data may be dependent on covariate data and, hence, "non-ignorable." To assess the probable type of missing data, baseline covariates among patients with and without missing data will be compared. If missing data are judged as Missing Completely at Random (MCAR), the typical strategy will be to conduct a complete case analysis, recognizing a loss of precision. The exception to this strategy will be when considerable data (i.e. >15%) are missing on a particular covariate that is judged to be critical for inclusion in the analysis. In this instance, imputation by unconditional or conditional mean imputation will be used; these simple approaches perform well when the overall percent of missing data is low. In rare instances when the percentage of missing data is not low (i.e. >15%), more sophisticated multiple imputation methods may be employed. Imputation methods will not be used to fill in values for missing outcome data.

[figure not shown]

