### **Hypothesis 1: Outcome Variables Main Effects for Community Re-integration Factors**

This algorithm is based on the assumption that an interaction between the intervention group and control groups can be modeled as a fixed effect. An LMM will then be used to evaluate whether the intervention had an effect at any time point or whether the intervention influenced change (growth, trajectory) in the outcome over the course of the study. The following will be considered for the analytical strategy:

- ANOVA, Repeated-measures ANOVA as well as MANCOVA will be used to compare the effect of the COMPASSgoal intervention vs. supported discharge group determined via baseline assessment. ANOVA will be used to compare the change from pre- to post-intervention between the two groups. Furthermore, in order to analyze the main effect of the COMPASSgoal intervention over time, a two-way repeated measures parametric ANOVA, as well as a non-parametric repeated measures Friedman ANOVA, will be performed, using the baseline time point, levels of TBI self-efficacy, or real-world tasks performance as the dependent variables. The levels of the repeated measures factor correspond to the number of assessments: baseline (pre-intervention) and 2 months post-intervention. The between-groups factor will be the intervention group vs. the supported discharge group. MANCOVA analysis will focus on the contrast in TBI self-efficacy between the intervention and supported discharge groups while accounting for a specified covariate: level of executive impairment as defined by FrSBE. In the case of non-normal residuals, we will use a nonparametric repeated measures approach. In the case of missing data, an LMM, which uses a maximum likelihood estimate to correct for unequal number of measures per subject, will be employed.
- *We will use Linear mixed models to control for potential confounding variables and baseline values will be utilized as a covariate. These models will allow for the additional control of potential within subjects clusters. These clusters, though not part of the formal hypothesis testing but byproducts of these models, will allow for conceptualization of additional future hypotheses.*

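### The complete-case rule for data judged MCAR is undefined and competes with the mixed model, and mean imputation is mandated above the plan's own limit for low missingness

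*Combined protocol and SAP*

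**What the plan says.** The Missing Data section of the SAP expects that loss may be informative: "sicker patients and those with sub-optimal treatment results may opt to discontinue participating". To judge the type of missingness, "baseline covariates among patients with and without missing data will be compared"; no test, threshold or decision rule follows. It then states: "If missing data are judged as Missing Completely at Random (MCAR), the typical strategy will be to conduct a complete case analysis".

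The one stated exception is "when considerable data (i.e. >15%) are missing on a particular covariate that is judged to be critical for inclusion in the analysis". There, "imputation by unconditional or conditional mean imputation will be used; these simple approaches perform well when the overall percent of missing data is low". The next sentence reads: "In rare instances when the percentage of missing data is not low (i.e. >15%), more sophisticated multiple imputation methods may be employed". The section ends on outcomes: "Imputation methods will not be used to fill in values for missing outcome data".

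The Hypothesis 1 section has its own rule: "In the case of missing data, an LMM, which uses a maximum likelihood estimate to correct for unequal number of measures per subject" is to be employed, with no condition on the missingness mechanism. That section also takes baseline as a covariate in the LMM and asks about an effect at any visit, but gives its repeated-measures factor two levels, baseline and post-intervention. The SAP Overview lists three visits. The Hypothesis 2 section fits an LMM that keeps cases with gaps, and assigns categorical outcomes to generalised estimating equations (GEE).

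**The concern.** Write T1, T2 and T3 for baseline, post-intervention and 3-month follow-up. Three things look wrong.

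- **Competing rules.** A dataset with missing outcome scores that is judged MCAR can go to a complete-case analysis or to the LMM. Nothing says which, or which visits and variables make a case complete. The choice could be made after the data are seen.
- **A check that looks in the wrong place.** The section fears dropout driven by poor treatment results, which arise after baseline, but judges the mechanism on baseline covariates. A Veteran who leaves after T2 has an informative T2 score on file that the check never uses.
- **A covariate rule at odds with its reason.** The same figure of 15% triggers mandatory mean imputation and marks the level at which missingness is no longer low.

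At stake are the 3-month comparison, possibly the T2 comparison, and the mediator relations in Hypothesis 2.

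**Working it through.** **1. The plan's own figure.** Power and sample size section: standardised effect 0.71, SD 7, two-sided 0.05, 90% power, 44 per group, 55 after 20% loss. The exact t solution is 42.7, so 43 per group; power at 44 is 0.909; 44 / 0.80 = 55. The figure reproduces and is not disputed. In points the effect is 0.71 x 7 = 4.97, about 5.

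**2. What the baseline check can see.** As an illustration, take one two-sample t-test at 0.05 comparing 22 Veterans with missing data (20% of 110) and 88 without. The noncentrality is d x sqrt(22 x 88 / 110) = 4.20d. Power is 24% at d = 0.3 and 55% at d = 0.5; 80% needs d = 0.67. In the simulations below, the check flags 4-6% of trials when loss follows the T2 result given baseline, which is its false-alarm rate, and 8-25% when loss follows the T2 score or change.

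**3. Size of the outcome rule.** Assumed, not in the documents: three equally correlated visits (r = 0.5 or 0.7); change SD 7; 20% total loss per arm; COMPASS-arm loss after T2 driven by poor T2 results (logit slope 0.7 or 1.0 per SD); control loss and any loss before T2 at random. The likelihood estimate regresses T2 on group and baseline in all with a T2 score, and T3 on group, baseline and T2 in those observed. Bias is in points, in favour of COMPASS.

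| Loss before T2 / after T2 | T2 bias, all-three-visit complete cases | Type I error at T2 | T3 bias, complete cases |
|---|---|---|---|
| 0% / 20% | 0.6 to 1.2 | 7-14% | 0.2 to 0.5 |
| 10% / 10% | 0.3 to 0.7 | 5-9% | 0.1 to 0.3 |
| 15% / 5% | 0.2 to 0.4 | 5-6% | 0 to 0.16 |
| 20% / 0% | none | nominal | methods coincide |

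The remaining results are for all loss after T2.

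- The all-visit likelihood analysis is within 0.07 at T3. Using every T2 score is within 0.05 at T2, with type I error 4.4-5.9%.
- Type I error at T3 hardly differs: 4.6-6.2% for complete cases, 4.0-5.3% for likelihood.
- With the same dropout rule in both arms there is no bias under no effect. With a 5-point effect, T3 complete cases are off by -0.06 to -0.26 and likelihood by at most 0.04.
- With COMPASS-arm loss driven by the unseen T3 score, both methods are off by 0.76 to 1.03.

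If complete means T1 and T2 only, the same Veterans enter either T2 analysis unless some return only at T3.

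**4. Precision if the data really are MCAR.** With 10-20% lost by T2 and 20% by T3, requiring all three visits raises the variance of the T1-to-T2 contrast by 3-15% (power 0.915 against 0.922-0.947, normal approximation).

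**5. The covariate rule.** Filling a fraction m of a covariate with its mean multiplies its SD by sqrt(1 - m): sqrt(0.85) = 0.92 and sqrt(0.80) = 0.89. Its correlation with an outcome shrinks by the same factor. In a simulated mediator with true indirect effect 0.35, 15% and 20% missing gave 0.29 and 0.28. For a baseline covariate under randomisation, with true effect 0.71 and values missing at random, the estimate stayed at about 0.71. Residual variance rose from 0.64 to 0.69-0.75 at 15-30% missing, so the SE rises by a factor of sqrt(0.69/0.64) to sqrt(0.75/0.64), or 1.04 to 1.08.

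**The case against.** The only exception to complete-case analysis concerns a covariate, and outcome imputation is barred. The rule may therefore govern covariates while the LMM governs outcomes. That is possible, but it is not written, and the lead-in to the rule is about missing outcome data. The text is ambiguous rather than plainly contradictory.

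A reader might infer that the powered comparison is biased, with type I error of 7-14%. The documents do not support this. The powered contrast is T1 to T2, and the Hypothesis 1 repeated factor has exactly those two levels, so a two-visit meaning is natural. The sample size section also applies the 20% loss to that contrast, which points to loss by T2. The section on patient retention plans engagement reminders between T2 and T3; it does not forecast that loss falls there. Material bias further needs outcome-driven loss in one arm only.

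A reader might also infer that outcomes not judged MCAR have no method. They do: the LMM of the Hypothesis 1 section.

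Nor does mean imputation spoil the randomised comparison. For a baseline covariate the cost is a little precision. The permitted conditional version was not evaluated for mediators; the attenuation shown is for the unconditional one. A per-covariate versus overall reading of the two 15% sentences is possible, but unstated.

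Finally, the likelihood figures rest on the factored estimate. A 300-trial check with a fitted random-intercept LMM gave T3 biases of -0.15 and +0.09 (simulation SE 0.07-0.08), too imprecise to confirm them closely.

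**Conclusion.** The point holds as a defect in the rules. Two outcome rules stand without precedence, complete case is undefined, the baseline check cannot reveal the dropout the section fears, and mandatory mean imputation rests on a rationale that its own threshold defeats.

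The size is conditional. It is essentially nil for the powered contrast on a two-visit reading. On a three-visit reading it runs from nil to about 1.2 points at T2, and at T3 from nil to about 0.5, depending on how much of the assumed 20% loss falls after T2 and on one-sided, outcome-driven dropout. For covariates, the harm falls on Hypothesis 2 mediators if the unconditional mean is used. The plan should be changed before analysis, but the point does not invalidate the design or the sample size.

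**What to change.** - Delete the MCAR/complete-case rule for outcomes. State that continuous outcomes are analysed by the Hypothesis 1 LMM on all available visits, with baseline as covariate and a group-by-visit term, whatever the baseline comparison shows. Keep that comparison as description.
- Leave categorical outcomes with the GEE of the Hypothesis 2 section, on all available data.
- Replace the two 15% sentences with one: multiple imputation for any critical covariate or mediator with more than 15% missing, counted per covariate.
- Add one not-at-random sensitivity analysis that fills in no outcome values, so the bar on outcome imputation can stand. Subtract (share of the COMPASS arm missing) x (shift) from the LMM difference, and raise the shift in 1-point steps until the interval includes 0. With 20% missing, each point of shift moves the difference by 0.2. For a 5-point difference and an assumed SE of 1.28 to 1.37, the shift needed is (5 - 1.99 x 1.28)/0.2 = 12.3 down to (5 - 1.99 x 1.37)/0.2 = 11.4 points.

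The cost is SAP wording and minor programming, with no new data. The LMM regains little for Veterans with no post-baseline score and does not correct dropout on unseen results; only the shift analysis addresses the latter. The nonparametric route for non-normal residuals would still need its own statement of which visits it uses.
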